6.5 STUDY INTERVENTION COMPLIANCE

- IMP accountability:
 - Intervention units are returned by the participant at each on-site visit. In case of DTP process, the intervention units can be returned by the carrier (if defined in the contract)
 - The Investigator counts the units remaining in the returned packs, and fills in the Intervention Log Form
 - The Investigator records the dosing information on the appropriate page(s) of the eCRF.
 - Also, a diary will be completed by the participant at each IMP administration.
 - The monitor in charge of the study then checks the eCRF data by comparing them with the IMP which he/she has retrieved and intervention log forms
 - Proper placement of tear-off label for accounting purposes
 - For SC injections, participants will be given training during the randomization period to ensure that the participant accepts the route of administration (participant will not be randomized if not comfortable with SC injections).

Compliance with study intervention will be assessed at each visit. Compliance will be assessed by direct questioning, counting of returned units in the pen devices during the site visits and documented in the source documents and relevant form. Deviation(s) from the prescribed dosage regimen should be recorded.

A record of the quantity of study intervention dispensed to and administered by each participant must be maintained and reconciled with study intervention and compliance records. Intervention start and stop dates, including dates for intervention delays and/or dose reductions will also be recorded.

6.6 CONTINUED ACCESS TO INTERVENTION AFTER THE END OF THE STUDY

There will be no access to study intervention or any additional care provided after the end of the study.

6.7 MANAGEMENT OF OVERDOSE

For this study, an overdose is defined as:

- For iGlarLixi: any dose corresponding to a lixisenatide daily dose greater than 40 µg (ie, >40 U [40 U insulin glargine / 40 µg lixisenatide] for 1:1 Pen, >80 U [80 U insulin glargine / 40 µg lixisenatide] for 2:1 Pen)
- For IDegAsp: any dose administration which, in the Investigator's opinion based on clinical judgment, is considered significantly greater than the prescribed dose of insulin,

- An overdose with metformin is defined as any dose greater than 2-fold above the recommended/planned or prescribed dose administered per day within this study.

In the event of an overdose, the Investigator should:

- Contact the Sponsor immediately.
- Evaluate the participant to determine, in consultation with the Sponsor, whether study intervention should be interrupted or whether the dose should be reduced.
- Closely monitor the participant for any AE/SAE and laboratory abnormalities until study intervention can no longer be detected systemically.
- Document appropriately in the CRF.

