- Pen-injector device: IDegAsp will be self-administered with FlexTouch®. The IDegAsp pen contains 3 mL of a sterile aqueous solution of 100 U/mL insulin Degludec and insulin Aspart with a ratio of 70:30.
- Route(s) of administration: subcutaneous (SC) injection
- Dose regimen:

IDegAsp will be self-administered once daily prior to the largest meal of the day according to the locally approved label. The injection time will be determined at the discretion of participants and Investigators on the day of randomization and should remain about the same until the end of the treatment period.

- Starting dose:

The recommended starting daily dose is 5 U -10 U based on Investigator's clinical judgement.

- Dose adjustment:

After the first week, dose will be adjusted weekly following same treat to target principle as for iGlarLixi. The titration algorithm recommended for iGlarLixi can be considered as

reference or titration can follow clinical practice as per investigator's discretion. Thereafter, until the end of the treatment the dose will be adjusted as necessary to maintain this fasting SMPG target. No dose cap will be set to the upper limit.

Non-investigational medicinal products (NIMP)

Background therapy metformin ± SGLT-2 inhibitor and rescue therapy are considered as non-investigational medicinal products (NIMPs).

Route(s) of administration: Oral administration for metformin and SGLT-2 inhibitor.

Dose regimen: Background treatments metformin ± SGLT-2 inhibitor will be administered orally according to the locally approved label. Metformin will be reimbursed by the Sponsor. A SU, a glinide, an alpha-GI, or a DPP-4 inhibitor, if previously taken, will be stopped at the randomization visit. Metformin is mandatory background therapy. Daily metformin dose will be maintained until the end of the treatment unless there is a specific safety issue related to this treatment. SGLT-2 inhibitors, if previously taken, should be continued at stable dose throughout the treatment period unless there is a specific safety issue related to this treatment.

- Formulation: consistent with local labelling

Posttrial access to study medication: Not applicable

Duration of study intervention:

The total duration of study participation for each participant is up to 27 weeks which includes up to 2 weeks of screening, 24 weeks of treatment period and 3 days of follow up period.

Statistical considerations:

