6.1.4 Starting dose and dose modification

6.1.4.1 iGlarLixi

Starting dose:

iGlarLixi is to be initiated with the 1:1 Pen. The recommended starting daily dose is 5 dose steps (5 U insulin glargine / 5 µg lixisenatide). A higher starting daily dose up to 10 dose steps (10 U insulin glargine / 10 µg lixisenatide) may be allowed in some cases according to the investigator's clinical judgment that a higher starting dose of iGlarLixi is considered necessary.

A starting daily dose greater than 10 dose steps (10 U insulin glargine / 10 µg lixisenatide) is not allowed, in order not to exceed the recommended starting dose of lixisenatide which is 10 µg.

Dose adjustment:

- After the first week, doses will be titrated once a week according to the dose adjustment algorithm described in [Table 5](#) to achieve glycemic target of fasting SMPG ≥ 80 and ≤ 100 mg/dL (≥ 4.4 and ≤ 5.6 mmol/L) while avoiding hypoglycemia.
- Thereafter, until the end of the treatment period, the dose will be adjusted as necessary to maintain this fasting SMPG target. A total daily dose greater than 40 dose steps (40 U insulin glargine / 20 µg lixisenatide) is not allowed. Doses may be modified at any time for hypoglycemia.

Dose modification will be based on a median of fasting SMPG values from the last 3 measurements, which may include the value measured on the day of titration, measured by the participant using glucometers and accessories supplied by the Sponsor for this study.

Table 5 - Dose adjustment algorithm for iGlarLixi

| Median of fasting SMPG values from the last 3 measurements, which may include the value measured on the day of titration | iGlarLixi dose adjustments (dose step/day) |
|---|--|
| >140 mg/dL (>7.8 mmol/L) | + 4 |
| >100 and ≤ 140 mg/dL (>5.6 and ≤ 7.8 mmol/L) | + 2 |
| Glycemic target: ≥ 80 and ≤ 100 mg/dL (≥ 4.4 and ≤ 5.6 mmol/L) | No change |
| ≥ 60 and <80 mg/dL (≥ 3.3 and <4.4 mmol/L) | - 2 |
| <60 mg/dL (<3.3 mmol/L) or occurrence of 2 (or more) symptomatic hypoglycemic episodes or one severe hypoglycemic episode (requiring assistance) documented in the preceding week | - 2 to -4 or at the discretion of the Investigator or medically qualified designee |

Median refers to intermediate SMPG value (the value between the lowest and the highest SMPG values when the values are ranked in a growing order).

Note: Choice of pen-injector for iGlarLixi:

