8.3.6 Adverse event of special interest

Adverse event of special interest

An AESI is an AE (serious or nonserious) of scientific and medical concern specific to the Sponsor's product or program, for which ongoing monitoring and immediate notification by the Investigator to the Sponsor is required. Such events may require further investigation in order to characterize and understand them.

The following are considered Adverse events of special interest:

- Pregnancy of a female participant entered in a study as well as pregnancy occurring in a female partner of a male participant entered in a study with IMP/NIMP.
 - Pregnancy occurring in a female participant entered in the clinical trial or in a female partner of a male participant entered in the clinical trial. It will be qualified as an SAE only if it fulfills one of the seriousness criteria (see Appendix 3 [Section 10.3]).
 - In the event of pregnancy in a female participant, IMP should be discontinued.
 - Follow-up of the pregnancy in a female participant or in a female partner of a male participant is mandatory until the outcome has been determined (See Appendix 4 [Section 10.4]).
- Symptomatic overdose (serious or nonserious) with IMP/NIMP
 - An overdose (accidental or intentional) with the IMP/NIMP is an event suspected by the Investigator or spontaneously notified by the participant (not based on systematic pills count) and defined as per Section 6.7.
- Increase in alanine transaminase (ALT) more than 3 times the ULN

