
• Pregnancy of a female participant entered in a study as well as pregnancy occurring in a female partner of a male participant entered in a study with IMP/NIMP
- Pregnancy occurring in a female participant entered in the clinical trial or in a female partner of a male participant entered in the clinical trial. It will be qualified as an SAE only if it fulfills one of the seriousness criteria.- In the event of pregnancy in a female participant, IMP should be discontinued.- Follow-up of the pregnancy in a female participant or in a female partner of a male participant is mandatory until the outcome has been.• Symptomatic overdose (serious or nonserious) with IMP/NIMP
- An overdose (accidental or intentional) with the IMP/NIMP is an event suspected by the Investigator or spontaneously notified by the participant (not based on systematic pills count).• Increase in alanine transaminase (ALT) more than 3 times the ULN	e-CRF specific tick box on the AE page

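### Protocol Section 6.7 defines iGlarLixi overdose only by an absolute lixisenatide limit, so an insulin error of up to 8 times the prescribed dose need not trigger the overdose actions or the AESI notice

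*Protocol*

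**What the plan says.** Protocol Section 6.7 gives three overdose definitions.

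- **iGlarLixi:** "For iGlarLixi: any dose corresponding to a lixisenatide daily dose greater than 40" µg, with the equivalents of more than 40 U (1:1 Pen) and more than 80 U (2:1 Pen).
- **IDegAsp:** a dose that, in the investigator's clinical judgment, "is considered significantly greater than the prescribed dose of insulin".
- **Metformin**, background in both arms: "any dose greater than 2-fold above the recommended/planned or prescribed dose administered per day".

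An overdose obliges the investigator to act: "Contact the Sponsor immediately", consult on interrupting or reducing treatment, and monitor closely. Section 8.3.6 makes symptomatic overdose an adverse event of special interest (AESI), "not based on systematic pills count) and defined as per Section 6.7". Section 8.3.1 requires AESIs to reach the sponsor within 24 hours.

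SAP Section 3.6.2 (Table 6) selects AESIs from a tick box on the adverse-event page. It describes overdose as "an event suspected by the Investigator or spontaneously notified by the participant (not based on systematic pills count") and does not repeat the reference to Section 6.7.

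**The concern.** iGlarLixi carries two active components, and the overdose definition follows only one of them. An excess of insulin glargine counts only when it also takes lixisenatide past 40 µg. The comparator, also an insulin product, is judged against what the participant was told to inject.

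The limit is loosest when the prescribed dose is lowest. Section 6.1.4.1 states "The recommended starting daily dose is 5 dose steps", and participants then are new to the pen. The protocol's own risk table (Section 2.3.1) lists medication-error overdose as a risk.

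What is at stake is a safety trigger: whether a site must call the sponsor, review the dose and monitor the participant after a large insulin error. Secondarily, the symptomatic-overdose rows of the AESI table rest on different definitions in the two arms.

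**Working it through.** **Inputs.** Pen concentrations and ranges come from Protocol Section 6.1.1: the 1:1 Pen has 100 U/mL and 100 µg/mL, for 5 to 20 steps; the 2:1 Pen has 100 U/mL and 50 µg/mL, for 21 to 40 steps. The recommended start is 5 steps, up to 10 are allowed, and the maximum is 40 steps or 20 µg (Section 6.1.4.1). The limit of 40 µg comes from Section 6.7.

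**The plan's own figures reproduce.** On the 1:1 Pen, 1 U carries 1 µg, so 40 µg is 40 U. On the 2:1 Pen, 1 U carries 0.5 µg, so 40 µg is 40 / 0.5 = 80 U. The limit is 40 / 20 = 2 times the protocol maximum for lixisenatide.

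**Multiple of the prescribed dose that must be exceeded**, correct pen used: limit in U divided by prescribed steps.

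| Prescribed steps | Pen | Limit (U) | Multiple |
|---|---|---|---|
| 5 | 1:1 | 40 | 40/5 = 8.0 |
| 10 | 1:1 | 40 | 40/10 = 4.0 |
| 15 | 1:1 | 40 | 40/15 = 2.7 |
| 20 | 1:1 | 40 | 40/20 = 2.0 |
| 21 | 2:1 | 80 | 80/21 = 3.8 |
| 30 | 2:1 | 80 | 80/30 = 2.7 |
| 40 | 2:1 | 80 | 80/40 = 2.0 |

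The multiple runs from 2 to 8. It is 4 to 8 over the permitted starting doses.

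**Worked case.** A participant prescribed 5 U injects 40 U from the 1:1 Pen. The excess is 40 − 5 = 35 U of glargine, 8 times the prescribed dose. Lixisenatide is exactly 40 µg, which is not greater than 40 µg, so this is not an overdose. An injection of 20 U against 5 U (4-fold), still inside the 1:1 Pen's range, is not one either. Either error with IDegAsp is an overdose if the investigator judges it significantly above prescription.

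**Conflict with the dose ceiling.** Section 6.1.4.1 forbids more than 40 steps. On the 2:1 Pen, 41 U carries 41 × 0.5 = 20.5 µg and 80 U carries 80 × 0.5 = 40 µg. All of 41 to 80 U breaks the ceiling without being an overdose.

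**Consequence.** Because Section 8.3.6 points back to Section 6.7, a symptomatic but non-serious iGlarLixi error at or below the limit requires neither the Section 6.7 actions nor the AESI notice. A serious one would still be reported within 24 hours as an SAE.

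**The case against.** The limit is not arbitrary. It is 2-fold the protocol maximum for lixisenatide. A product-specific ceiling also makes sense because IDegAsp has none: "No dose cap will be set to the upper limit". That stands, and it is why the limit should be kept.

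Much of the clinical content is captured elsewhere, in both arms:

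- Use errors with the pens are reportable (Protocol Section 6.1.1).
- Departures from the prescribed regimen are recorded (Section 6.5).
- Signs and symptoms of a suspected overdose are adverse events (Section 10.3.1).
- Hypoglycemia uses the same ADA levels in both arms (Section 8.3.7, SAP Section 3.6.3.2).

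This also stands. It limits the harm, but none of these routes carries the immediate sponsor contact of Section 6.7 or the 24-hour AESI notice.

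A reader might infer that the AESI table will undercount iGlarLixi overdoses relative to IDegAsp. The documents do not support that. They give no overdose frequency, and the IDegAsp criterion has no number attached. The SAP counts a tick box without citing Section 6.7, so a site may tick an event below the limit. It is equally tempting to apply metformin's 2-fold rule to iGlarLixi and call the doses in between missed. That rule governs neither injectable and is the same in both arms, so it says nothing about a between-arm difference.

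**Conclusion.** The gap is real but small. Followed as written, Section 6.7 lets an iGlarLixi insulin error of 2 to 8 times the prescribed dose, depending on the dose and pen, pass without the overdose actions or the AESI notice. The gap is widest at the recommended start.

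The multiples assume that the assigned pen is used. The documents do not state the largest dose a pen can deliver in one injection, so they do not show how easily the largest errors could occur. The number of affected events is unknown and could be near zero.

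The size and direction of any between-arm difference in AESI counts cannot be determined. Safety analyses are descriptive without testing (SAP Section 3.6), and no efficacy result, error rate or sample size depends on this point. It is a cheap improvement to safety reporting, not a defect that threatens the trial's conclusions.

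**What to change.** In Protocol Section 6.7, extend the iGlarLixi bullet with the criterion already used for IDegAsp: any dose that the investigator, on clinical judgment, considers significantly greater than the prescribed dose. Keep the limit of more than 40 µg lixisenatide as an alternative criterion. Section 8.3.6 then picks up the change through its existing cross-reference.

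The cost is one added clause, a note to sites and probably a few more AESI reports in the iGlarLixi arm. The criterion is subjective, and investigators know the treatment in this open-label trial (Section 6.4), but the plan already accepts that for IDegAsp. The definitions would become more similar, not identical, since the lixisenatide limit has no IDegAsp counterpart. An amendment during the trial (first randomization 18 July 2022, SAP version 1 approved 14 November 2023) would leave two definitions over time, which the report should state. A separate SAP row or a table footnote would add little by comparison.

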6.8 CONCOMITANT THERAPY

Any medication or vaccine (including over-the-counter or prescription medicines, recreational drugs, vitamins, and/or herbal supplements) that the participant is receiving at the time of enrollment or receives during the study must be recorded along with:

- Reason for use
- Dates of administration including start and end dates
- Dosage information including dose and frequency

The Sponsor should be contacted if there are any questions regarding concomitant or prior therapy.

6.8.1 Background therapy

Background treatments metformin ± SGLT-2 inhibitor are considered as NIMPs and will be administered orally according to local labeling. Metformin will be supplied or reimbursed by the Sponsor. An SU, a glinide, an alpha-GI, or a DPP-4 inhibitor, if previously taken, will be stopped before or on the randomization day (V2) for the participants who are eligible for randomization.

Metformin is mandatory background therapy. Daily metformin dose (at least 1000 mg or the maximum tolerated dose) should remain unchanged until the end of treatment period unless there is a specific safety issue related to this treatment.

SGLT-2 inhibitors, if previously taken, should be continued at the stable dose throughout the treatment period unless there is a specific safety issue related to this treatment.

The dose of metformin and SGLT-2 inhibitors is to be reported in the eCRF.

6.8.2 Allowed concomitant therapy

Any therapies or medications other than prohibited concomitant therapy in addition to the study intervention should be kept to a minimum during the study. However, if these are considered necessary for the participant's welfare and are unlikely to interfere with the study intervention, they may be given at the discretion of the Investigator, with a stable dose (when possible).

In the iGlarLixi treatment group, for oral medicinal products that are particularly dependent on threshold concentrations for efficacy, such as antibiotics, statins and oral contraceptives, participants should be advised to take those medicinal products at least 1 hour before or 11 hours after study intervention injection. Gastro-resistant formulations containing substances sensitive to stomach degradation should also be administered 1 hour before or 11 hours after injection of iGlarLixi.

Specific treatments, which are ongoing before the study and/or prescribed or changed during the study, must be recorded in the eCRF and source data.

6.8.3 Prohibited concomitant therapy

The following drugs are not permitted during the screening period and the 24-week randomized open-label treatment period:

- Any glucose-lowering agents other than the study interventions, authorized background antidiabetic therapy (metformin ± SGLT-2 inhibitor) and rescue therapy, if necessary.
- Note: Short time use (≤ 14 days) of short/rapid-acting insulin due to acute illness or surgery (eg, infectious disease) is allowed.
- Systemic glucocorticoids for more than 14 days (topical or inhaled applications are allowed).
- Body weight loss drugs which is defined as prescription medications with indication to treat overweight or obesity.
- Using any study interventional drugs other than those specified in this protocol.

After the last administration of study interventions during the study period, any antidiabetic treatments are permitted, as deemed necessary by the Investigator.

6.8.4 Rescue medicine

The date and time of rescue medication administration as well as the name and dosage regimen of the rescue medication must be recorded.

Routine central laboratory alerts on HbA1c are required to ensure that glycemic parameter results remain under predefined threshold value. In case HbA1c is above threshold ($\text{HbA1C} > 8\%$ at Week 12 or later on), the investigator will receive an alert issued by the central laboratory and should ensure that no reasonable explanation exists for insufficient glucose control and in particular that the study treatment is appropriately titrated according to the titration algorithm (up to a maximum of 40 dose steps [40 U insulin glargine / 20 μg lixisenatide] for iGlarLixi group; no upper limit for IDegAsp group), compliance to diet and lifestyle is appropriate, and there is no intercurrent disease, which may jeopardize glycemic control (eg, infectious disease)

If any of the above can reasonably explain insufficient glycemic control, the Investigator should take appropriate actions and retest the central lab HbA1C in 4 weeks at next visit or an unscheduled visit whichever suitable.

If the repeated HbA1c remains above 8% despite appropriate corrective actions or none of the above-mentioned reasons can be found and managed, a rescue therapy can be considered.

- For iGlarLixi group, rescue therapy can be considered if a daily dose >40 dose steps is necessary to decrease HbA1c below the threshold, or if any safety concerns (repeated hypoglycemia, severe gastrointestinal AE, etc) prevent up titration to reach 40 dose steps according to the Investigator's judgment.
- In both iGlarLixi and IDegAsp treatment groups, it is recommended to add one rapid/short-acting insulin; this should be started as a single daily administration to be given at a meal of the day as appropriately at the investigator's discretion.

No other GLP-1 RA or DPP-4 inhibitor or basal insulin, including pre-mixed insulin, should be used as rescue medication in either of the treatment groups.

Once rescue medication is considered as necessary as per the investigator's medical decision, the participant should be scheduled for a **Pre-rescue onsite visit**. Before initiating rescue therapy, all assessments (except 7-point SMPG) planned at the end of treatment visit are to be performed at the pre-rescue visit. After these assessments are completed and rescue therapy initiated, the participant will remain in the study and continue to administer the study treatment (including background therapies). The planned visits and assessments should be performed until the last scheduled visit.

7 DISCONTINUATION OF STUDY INTERVENTION AND PARTICIPANT DISCONTINUATION/WITHDRAWAL

The study intervention should be continued whenever possible. In case the study intervention is stopped, it should be determined whether the stop can be made temporarily; permanent study intervention discontinuation should be a last resort. Any study intervention discontinuation must be fully documented in the eCRF. In any case, the participant should remain in the study as long as possible.

